3.2. Subject Exclusion Criteria

If met, any of the following criteria will lead to subject exclusion from the study:

1. Transformed DLBCL or DLBCL with coexistent histologies (eg, follicular or mucosa-associated lymphoid tissue lymphoma).
2. PMBL.
3. Known CNS lymphoma (either primary or metastatic).
4. Autologous stem cell transplant within the previous 3 months, allogeneic stem cell transplant within the previous 6 months, or active graft versus host disease following allogeneic transplant.
5. Use of immunosuppressive therapy within 28 days of starting study treatment. Immunosuppressive therapy includes, but is not limited to, cyclosporine A, tacrolimus, or high-dose corticosteroids. Subjects receiving corticosteroids must be at a dose level ≤ 10 mg/day within 7 days of initiating study treatment.
6. Prior or concurrent therapy with a JAK inhibitor or BTK inhibitor.

7. Receipt of anticancer medications or investigational drugs within the following intervals before starting study treatment (unless otherwise approved by the sponsor):
 - a. < 6 weeks for mitomycin-C or nitrosoureas.
 - b. < 28 days for any investigational agent for any indication.
 - c. < 21 days or 5 half-lives (whichever is greater) for all other cytotoxic anticancer medications.
 - d. < 4 weeks for monoclonal antibodies used as anticancer treatment.
 - e. < 10 weeks or 5 half-lives from completion of any radio- or toxin-immunoconjugates.
8. Major surgery 28 days before starting study treatment.
9. Prior treatment-related toxicities that have not resolved to \leq Grade 1, with the exception of Grade \leq 2 neuropathy and any grade of alopecia.
10. Chronic or current active infectious disease requiring systemic antibiotics, antifungal, or antiviral treatment.
11. Clinically significant cardiac disease, including unstable angina, acute myocardial infarction, and/or cardiac conduction issues within 6 months of Day 1; New York Heart Association Class II to IV congestive heart failure; or uncontrolled arrhythmia.
12. Known bleeding disorders (eg, von Willebrand's disease) or hemophilia.
13. History of stroke or intracranial hemorrhage within 6 months before study entry.
14. Significant concurrent, uncontrolled medical condition including, but not limited to, renal, hepatic, hematological, gastrointestinal, endocrine, pulmonary, neurological, cerebral, or psychiatric disease.
15. Current or previous other malignancy within 3 years of study entry or not cured with treatment, except cured basal or squamous cell skin cancer, superficial bladder cancer, prostate intraepithelial neoplasm, carcinoma *in situ*, or other noninvasive or indolent malignancy without sponsor approval.
16. Subjects who are currently receiving therapy with a strong CYP3A4 inducer or inhibitor.
17. Subjects who are currently receiving therapy with warfarin or vitamin K antagonists, such as coumarin-based anticoagulants (eg, fluindione and phenindione).
18. Unable to swallow oral medication, malabsorption syndrome, disease significantly affecting gastrointestinal function, resection of the stomach or small bowel, ulcerative colitis, symptomatic inflammatory bowel disease, or partial or complete bowel obstruction.
19. Known human immunodeficiency virus infection.
20. Known hepatitis B virus (HBV) or hepatitis C virus (HCV) or at risk for HBV reactivation. Hepatitis B virus DNA and HCV RNA must be undetectable. At risk for HBV reactivation is defined as hepatitis B surface antigen (HBsAg) positive or anti-hepatitis B core (HBc) antibody positive.
21. Unwilling to be transfused with blood components.

22. Pregnant or breastfeeding women or subjects unwilling to take appropriate measures to avoid pregnancy.
23. Any condition that would jeopardize the safety of the subject or compliance with the Protocol.
24. Previous reaction to any component of or INCB039110 or ibrutinib, or known hypersensitivity to either active substance or any of their excipients.
25. Prior radiotherapy within 2 weeks before starting study treatment. A 1-week washout period is permitted for palliative radiation to non-central nervous system (CNS) disease with medical monitor approval.

4. INVESTIGATIONAL PLAN

4.1. Overall Study Design

This is an open-label, single-group, Phase 1/2 study of INCB039110 in combination with ibrutinib in subjects with relapsed or refractory DLBCL. Phase 1 will evaluate the safety and tolerability of INCB039110 when combined with ibrutinib in subjects with DLBCL (ABC, GCB, or unclassifiable) using a 6 + 3 design; Phase 2 will evaluate the efficacy of the combination in subjects with ABC or unclassifiable DLBCL at the dose determined in Phase 1 using a Simon 2-stage expansion design. Subjects may continue to receive study treatment until evidence of disease progression, unacceptable toxicity, or consent withdrawal.

4.1.1. Phase 1

[figure not shown]
The starting dose of INCB039110 will be 300 mg once daily (QD). Depending on tolerability, the dose of INCB039110 in combination with ibrutinib (560 mg QD) could be increased to 400 mg QD (Cohort 2) or decreased to 200 mg QD (Cohort -1). The dose selected for study in Phase 2 will be the dose tolerated by at least two-thirds of subjects who did not require a dose reduction within the first 28 days of treatment. In order to be included in the tolerability review, a subject must have received the cohort-specific dose of INCB039110 and ibrutinib for at least 75% of the days during the 28-day DLT surveillance period or have experienced a DLT. Additional subjects may be enrolled to achieve a minimum cohort size of 6 should withdrawal or dose interruptions/reductions result in a subject being nonevaluable.

Dose cohorts are outlined in [Table 3](#), and the design is depicted in [Figure 4](#).

Table 3: Phase 1 Dose Cohorts

Cohort	Number	Regimen	Subjects With DLT	Action
-1	6	INCB039110 200 mg QD + ibrutinib 560 mg QD	≤ 1	Begin expansion portion of the study
			2	Enroll 3 additional subjects (9 subjects total)
			≥ 3	Terminate study
1 (Starting dose)	6	INCB039110 300 mg QD + ibrutinib 560 mg QD	≤ 1	Escalate to Cohort 2
			2	Enroll 3 additional subjects (9 subjects total); if no new DLTs, escalate to Cohort 2
			≥ 3	Reduce to Cohort -1
2	6	INCB039110 400 mg QD + ibrutinib 560 mg QD	≤ 1	Begin Phase 2 study
			2	Enroll 3 additional subjects (9 subjects total); if no new DLTs, begin Phase 2 study
			≥ 3	Begin Phase 2 study using Cohort 1 dose

[figure not shown]
Figure 4: Phase 1 Design Schema

4.1.2. Phase 2

Subjects with ABC or unclassifiable DLBCL will receive the recommended Phase 2 dose (RP2D) of INCB039110 in combination with ibrutinib as determined in Phase 1. Phase 2 will use a Simon 2-stage design with a stopping rule to allow early termination of the study at the end of Stage 1 if there is lack of sufficient efficacy. During Stage 1, if 9 or fewer of the first 22 evaluable subjects achieve an objective response (defined as a CR or PR), then the study may be terminated. If 10 or more subjects achieve an objective response, then the study will continue and accrue 38 additional subjects to Stage 2. Subjects who were enrolled but did not receive treatment will be excluded from the efficacy analysis and replaced. A timely assessment of response will be made to avoid risk of overenrollment before accrual to Stage 2. At the end of Stage 2, ORR will be assessed for sufficient efficacy to warrant further study. The study will be considered successful if the total number of objective responders is 29 or more. The design is depicted in [Figure 5](#).

Figure 5: Phase 2 Design Schema

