Subjects with ABC or unclassifiable DLBCL will receive the recommended Phase 2 dose of INCB039110 combination with ibrutinib as determined in Phase 1. Phase 2 will use a Simon 2-stage design with a stopping rule to allow early termination of the study at the end of Stage 1 if there is lack of sufficient efficacy. During Stage 1, if 9 or fewer of the first 22 evaluable subjects achieve an objective response (defined as a CR or PR), then the study may be terminated. If 10 or more subjects achieve an objective response, then the study will continue and accrue 38 additional subjects to Stage 2. Subjects who were enrolled but did not receive treatment will be excluded from the efficacy analysis and replaced. A timely assessment of response will be made to avoid risk of overenrollment before accrual to Stage 2. At the end of Stage 2, ORR will be assessed for sufficient efficacy to warrant further study. The study will be considered successful if the total number of objective responders is 29 or more. The study will end once all subjects have discontinued study treatment.

Study Population:

Key Inclusion Criteria:

- Male or female, 18 years or older.
 - Histologically documented diagnosis of DLBCL.
 - For Phase 1, subjects may have any DLBCL subtype.
 - For Phase 2, subjects must have ABC or unclassifiable subtypes of DLBCL confirmed by immunohistochemistry using the Hans algorithm.
- Subjects having a computed tomography (CT) scan abnormality with uncertain interpretation following completion of the most recent treatment regimen must have biopsy confirmation of residual DLBCL before study entry.
- Relapsed or refractory DLBCL, defined as having received at least 1 but no more than 3 prior treatment regimens and ineligible for high-dose chemotherapy/autologous stem cell transplant.
 - Fluorodeoxyglucose-avid disease (based on local evaluation) per the Lugano Classification. Fluorodeoxyglucose-avid disease is defined as disease with a 5-point scale score of 4 or 5.
 - Subjects must have archived tumor tissue (block or 15-20 unstained slides) available, or be willing to undergo an incisional or excisional lymph node biopsy of accessible adenopathy (or, in less accessible lymph nodes, 4 to 8 core biopsies).

- At least 1 measurable (≥ 2 cm in longest dimension) lesion on CT scan or magnetic resonance imaging (MRI).
- Eastern Cooperative Oncology Group (ECOG) performance status 0 to 2.

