The study will lead to a decision between 2 prespecified hypotheses about the probability of an ORR, p . The null hypothesis H_0 : $p = 40\%$ reflects a response rate that would be of no clinical benefit, and the alternative hypothesis H_A : $p = 55\%$ is a response rate that might lead to larger, confirmatory studies. Using a Simon 2-stage optimal design, a total of 60 subjects will be needed for 80% power at 1-sided $\alpha = 0.1$ level. If there are 9 or fewer objective responders from the first 22 evaluable subjects, the null hypothesis will be considered as supported, and the study will be terminated. Otherwise, 38 additional subjects will be enrolled (Stage 2). Subjects who did not receive study treatment will be excluded from the analysis of Stage 1 and replaced.

Primary efficacy analysis: The study will be considered successful if the total number of objective responders is ≥ 29 in Phase 2. A 90% confidence interval will be calculated for the ORR.

Secondary efficacy [REDACTED] analysis: Median DOR and durable response rate (CR or PR ≥ 16 weeks) will be estimated with a 90% confidence interval. Median PFS will be estimated with 90% confidence intervals. [REDACTED]

Safety Analysis: Safety data will be tabulated with summary statistics.

TABLE OF CONTENTS

SYNOPSIS	3
LIST OF ABBREVIATIONS.....	16
1. INTRODUCTION	19
1.1. Overview of Diffuse Large B-Cell Lymphoma.....	19
1.1.1. Treatment for Advanced DLBCL	20
1.1.2. Treatment for Relapsed/Refractory DLBCL	21
1.2. Study Rationale.....	21
1.2.1. Inhibition of Janus Kinase as a Target for Cancer Therapy	21
1.2.2. Inhibition of JAK With INCB039110	23
1.2.3. Inhibition of Bruton's Tyrosine Kinase as a Target for Cancer Therapy.....	24
1.2.4. Combined Inhibition of JAK and BTK in DLBCL	25
1.3. Potential Risks and Benefits of the Treatment Regimen	26
1.3.1. INCB039110.....	26
1.3.2. Ibrutinib	27
1.3.2.1. Summary of Clinical Safety.....	27
1.3.2.2. Risks	28
1.3.2.3. Cytopenias	28
1.3.2.4. Atrial Fibrillation.....	28
1.3.2.5. Second Primary Malignancies	28
1.3.2.6. Tumor Lysis Syndrome	28
1.3.2.7. Diarrhea	29
1.3.2.8. Rash	29
1.3.2.9. Interstitial Lung Disease	29
1.3.3. Potential Risks and Benefits for the Combination of INCB039110 and Ibrutinib	29
2. STUDY OBJECTIVES AND ENDPOINTS.....	30
2.1. Study Objectives.....	30
2.1.1. Phase 1	30
2.1.1.1. Primary Objective.....	30
2.1.1.2. Secondary Objective.....	30
██████████	30
2.1.2. Phase 2.....	30

2.1.2.1.	Primary Objective.....	30

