9.2.2. Sample Size in Expansion Phase

The study will lead to a decision between 2 prespecified hypotheses about the probability of an ORR, p . The null hypothesis H_0 : $p = 40\%$ reflects a response rate that would be of no clinical benefit, and the alternative hypothesis H_A : $p = 55\%$ is a response rate that might lead to larger, confirmatory studies. Using a Simon 2-stage optimal design, a total of 60 subjects will be needed for 80% power at 1-sided $\alpha = 0.1$ level. If there are ≤ 9 objective responders from

the first 22 evaluable subjects, then this will support the null hypothesis, and the study will be terminated. Otherwise, 38 additional subjects will be enrolled (Stage 2).

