9.4. Statistical Analyses

9.4.1. Primary Analyses

The primary endpoint is ORR; a subject will be considered as a responder if his or her best overall response is PR or better based on the Lugano Classification (Cheson et al 2014). The rate of responders will be estimated using the observed rate, and its 90% CI will be calculated using the method of Koyama and Chen (2008) that accounts for the early termination rules of the Simon 2-stage design. The study will be considered successful if the total number of objective responders is ≥ 29 in Phase 2.

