9.5. Interim Analysis

No interim analysis is planned.

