7.3. Analysis of the Primary Efficacy Parameter

7.3.1. Primary Efficacy Analysis

The primary variable for the Phase 2 of the study is ORR, which is defined as the proportion of subjects with best response (CR or PR) by modified Lugano Classification ([Cheson et al 2014](#)) for DLBCL. The proportion of responders within each treatment group will be estimated with 90% CIs by treatment group. Confidence intervals will be calculated based on the method of Koyama and Chen ([2008](#)) that accounts for early termination rules of the Simon 2-stage design. Within each treatment group, 1- sample binomial test will be used to test the null hypothesis.

In general, best response is determined on the subject level using the highest overall response achieved postbaseline. In the case of SD, measurements must meet the SD criteria at least once after study entry at a minimum interval of 56 days. Subjects who fail to meet these criteria will have best response of PD if the next available Lugano Classification evaluation after the initial scan indicates PD or NE if no additional evaluations are available.

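### The Stage 1 futility stop at 9 or fewer of 22 is optional in some sections and mandatory in others, and the 10% level with success at 29 of 60 is guaranteed only if it is mandatory

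*Protocol*

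**What the plan says.** The same Stage 1 result, 9 or fewer responders among the first 22 evaluable subjects, has two different consequences.

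| Document | Optional | Mandatory |
|---|---|---|
| Protocol Synopsis | Overall Study Design, Phase 2: "then the study may be terminated" | Sample size determination: "the null hypothesis will be considered as supported, and the study will be terminated" |
| Protocol body | 4.1.2: "of the first 22 evaluable subjects achieve an objective response (defined as a CR or PR), then the study may be terminated" | 9.2.2: "then this will support the null hypothesis, and the study will be terminated" |
| SAP | 3.1.2, same wording as Protocol 4.1.2 | 3.3.2, same wording as Protocol 9.2.2 |

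Success is 29 or more responders in total (Synopsis; Protocol 4.1.2 and 9.4.1; SAP 3.1.2). The significance level is one-sided 10% (Protocol 9.3, SAP 3.2). The 90% confidence interval for the response rate uses the Koyama and Chen method, described in Protocol 9.4.1 as one "that accounts for the early termination rules of the Simon 2-stage design" and in almost the same words in SAP 7.3.1. Protocol 9.5 and SAP 9 both state: "No interim analysis is planned".

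**The concern.** A futility stop that may be overridden does no harm to the type I error when the final cut-off was set without taking credit for it. Here credit was taken: 29 of 60 is the Simon optimal cut-off, and it meets 10% only because trials with 9 or fewer Stage 1 responders cannot go on to succeed. If some of those trials may continue and still claim success at 29, the false-positive rate rises. The confidence interval has the same problem, because it is computed as though the stop is obeyed.

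At stake are the error rate of the go/no-go decision, the validity of the interval reported with it, and up to 38 further subjects treated after a failed Stage 1. The study is open-label, so if the conflict is left until Stage 1 reads out, the sponsor would be choosing the rule with the responses in view. The clause is likely to matter: at a true rate of 40%, 62% of trials fall at or below 9/22.

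The statement that no interim analysis is planned is a labelling slip, since the 22-subject look is one. It has no effect on alpha.

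**Working it through.** **Inputs.** Null rate 0.40, alternative 0.55, one-sided level 0.10, power 80% and total 60 (Protocol 9.2.2 and 9.3); stages of 22 and 38 (Protocol 4.3.1); stop at 9 or fewer; success at 29 or more (Protocol 4.1.2).

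**Formula.** Let X1 ~ Bin(22, p) and X2 ~ Bin(38, p). If the study continues whenever X1 ≥ c, the chance of declaring success is

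P(c, p) = Σ over x from c to 22 of P(X1 = x) × P(X2 ≥ 29 − x).

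The binding rule is c = 10. Always overriding exactly 9/22 is c = 9. Never stopping is c = 0, which equals P(Bin(60, p) ≥ 29).

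**1. Reproduce the plan.** With c = 10, P = 0.0949 at p = 0.40 and 0.8004 at p = 0.55, so the stated 10% and 80% hold. An exhaustive search over totals from 40 to 74 returns this design (stop at ≤9/22, success at ≥29/60) as the optimal one, with expected sample size under the null of 22 + 38 × (1 − 0.6244) = 36.3.

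**2. Relax the stop, keeping 29.**

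| Conduct after ≤9/22 | Type I error (p = 0.40) | Power (p = 0.55) |
|---|---|---|
| Always stop | 0.0949 | 0.8004 |
| Continue at exactly 9 | 0.1082 | 0.8486 |
| Never stop | 0.1184 | 0.8784 |

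The 9/22 contribution at p = 0.40 is P(X1 = 9) × P(X2 ≥ 20) = 0.1703 × 0.0784 = 0.0133, and 0.0949 + 0.0133 = 0.1082. If the stop is never applied, all 60 subjects are enrolled, against 36.3 expected under the null.

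**3. How much overriding takes alpha past 10%?** Unrounded values were used in the divisions.
- Any crossing, overridden at random: (0.1000 − 0.0949) / (0.1184 − 0.0949) = 0.218.
- Only 9/22 overridden: (0.1000 − 0.0949) / (0.1082 − 0.0949) = 0.385.

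**4. Confidence interval.** Assumption: the lower 90% limit at 29/60 is the p that solves P(X1 ≥ 10 and total ≥ 29) = 0.05. This gives 0.3786. At that true rate, the chance of 29 or more is 5.0% with the stop applied, 5.7% if 9/22 is always overridden and 6.3% if the stop is never applied. On this construction the limit loses its nominal 5% tail once overrides occur.

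**5. A cut-off for a non-binding stop.** With success at 30 or more of 60:

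| Conduct after ≤9/22 | Type I error | Power |
|---|---|---|
| Always stop | 0.0630 | 0.7567 |
| Continue at exactly 9 | 0.0700 | 0.7961 |
| Never stop | 0.0746 | 0.8183 |

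Alpha stays below 10% however the stop is used, but power can fall short of 80%.

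**The case against.** The best defence is that the plan leans towards a binding stop. The sections that state alpha and power carry the mandatory wording, and they enrol Stage 2 only when the stop is not met. Even the optional sections describe accrual to Stage 2 only after 10 or more responses, and the interval method fits the same reading. The Phase 2 schema figures are not visible and might show the branch. This makes the mandatory reading the likelier intention. It does not remove the conflict: the sections that describe how Phase 2 is run, Protocol 4.1.2 and SAP 3.1.2, expressly allow discretion.

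The effect is also small. Passing 10% takes repeated overrides, the likeliest one (at exactly 9/22) gives 10.8%, and the plan calls its level acceptable for proof of concept. That stands and limits the severity. Overriding crossings at random, whatever the response count, is an unlikely pattern; the 9/22 threshold is the more realistic one.

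SAP 7.3.1 also names a one-sample binomial test without saying how it treats the two stages. If it is an ordinary test on 60 subjects, 29 responders give p = 0.118 and 30 give p = 0.075, so that test would hold 10% even with no stop. This stands as a limit on the claim: the figures here concern the rule of success at 29 or more, which the Protocol uses to declare success.

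Finally, the documents do not say whether Stage 1 had been read by the time of the current SAP (29 NOV 2022), so it cannot be assumed that the conflict can still be settled blind to the result.

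**Conclusion.** The concern holds. The Synopsis, the Protocol body and the SAP each contradict themselves on whether 9 or fewer of 22 ends the study. The stated one-sided 10% with success at 29 of 60 is guaranteed only under the mandatory wording. Type I error is 9.5% if the stop is binding and at most 11.8% if it is never applied. The type I error and power figures are exact binomial results from the plan's own inputs. The interval figures rest on the construction stated in the working. The excess is modest but affects the primary decision rule, and it should be fixed.

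**What to change.** **Preferred: make the stop binding.** In the Synopsis design text, Protocol 4.1.2 and SAP 3.1.2, change *may* to *will* so that they match the Synopsis sample-size text, Protocol 9.2.2 and SAP 3.3.2. Keep the cut-off of 29. For consistency, reword Protocol 9.5 and SAP 9 to say that no interim analysis is planned other than the binding Stage 1 futility analysis of the first 22 evaluable subjects. Sample size, cut-off, power and interval method do not change.

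The cost is three wording changes and two labelling edits, with the sponsor and IRB/IEC approval that Protocol 10.1 requires for protocol changes, and the loss of discretion after a failed Stage 1. At a true rate of 55%, the binding stop ends 13.3% of trials at Stage 1, 7.1 points of that at exactly 9/22. That loss is already counted in the 80% power.

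**Alternative: keep discretion.** Declare the stop non-binding in all six places and re-derive the cut-off, the operating characteristics and the interval method. As an example, 30 of 60 caps alpha at 7.5%, but power ranges from 75.7% with the stop always applied to 81.8% with it never applied, so the stated 80% may be missed at this sample size.

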4.2. Measures Taken to Avoid Bias

Measurements of safety and efficacy will be objectively assessed using NCI CTCAE v4.03 (NCI 2010) and Lugano Classification (Cheson et al 2014), respectively.

4.3. Number of Subjects

4.3.1. Planned Number of Subjects

Up to 18 subjects will be enrolled in Phase 1, and approximately 60 subjects will be enrolled in Phase 2 (22 in Stage 1 and 38 in Stage 2).

4.3.2. Replacement of Subjects

Additional subjects may be enrolled in Phase 1 to achieve a minimum cohort size of 6 should withdrawal or dose interruptions/reductions result in a subject being nonevaluable.

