5.5. Treatment Interruptions and Adjustments

5.5.1. Dose Modifications

5.5.1.1. Dose Modification of INCB039110

Treatment with INCB039110 may be delayed up to 2 weeks (14 days) to allow for resolution of toxicity. Subjects may resume treatment if no medical condition or other circumstance exists that, in the opinion of the investigator, would make the subject unsuitable for further participation in the study. The treating investigator should contact the sponsor to discuss the case of any subject whose treatment has been delayed for more than 14 days before restarting treatment with INCB039110.

Because subjects may enter the study with extensive pretreatment and/or severe bone marrow infiltration by the primary disease, dose interruption and reduction rules are provided as guidelines (see Table 4 and Table 5). Individual decisions regarding dose reduction should be made using clinical judgment and in consultation with the sponsor's medical monitor, taking into account relatedness of the AE to the study drug and the subject's underlying condition. Adverse events that have a clear alternative explanation or transient (≤ 72 hours) abnormal laboratory values without associated clinically significant signs or symptoms may be exempt from dose-reduction rules.

Table 4: Guidelines for Interruption and Restarting Study Drug

ADVERSE EVENT	ACTION TAKEN
Chemistry	

 • AST and/or ALT $> 3.0 \times \text{ULN}$ Note: In subjects with bone metastasis-related elevations at baseline, contact sponsor to discuss clinical management and possible dose reductions.	
Step 1: Interrupt INCB039110 up to 14 days until the toxicity has resolved to \leq Grade 1 (unless approved otherwise by the medical monitor).
 
Step 2: Restart INCB039110 at same dose. If assessed as related to INCB039110, restart at next lower dose. Monitor as clinically indicated.

Hematology	

 • ANC $\leq 1.0 \times 10^9/\text{L}$ unless due to underlying disease • Platelet count is $< 60 \times 10^9/\text{L}$ unless due to underlying disease 	
Step 1: Interrupt INCB039110 up to 14 days until the toxicity has resolved to \leq Grade 1 or pretherapy baseline.
 
Step 2: Restart INCB039110 at same dose; monitor as clinically indicated.

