5.5.2. Dose-Limiting Toxicity and Determination of Recommended Phase 2 Dose

A DLT will be defined as the occurrence of any toxicities in [Table 7](#) occurring up to and including Study Day 28, except those with a clear alternative explanation (eg, disease progression) or transient (\leq 72 hours) abnormal laboratory values without associated clinically significant signs or symptoms based on investigator determination. All DLTs will be assessed by the investigator using CTCAE v4.03 criteria ([NCI 2010](#)). In order to be included in the tolerability review, subjects must have received the cohort-specific dose of INCB039110 and ibrutinib for at least 75% of the days during the 28-day surveillance period or have experienced a DLT. Additional subjects may be enrolled to achieve a minimum cohort size should withdrawal or dose interruptions/reductions result in subjects being nonevaluable.

Individual subject dose reductions may be made based on events observed at any time during treatment with study drug; however, for the purposes of dose cohort escalation/de-escalation, expanding a dose cohort, and determining the RP2D, decisions will be made based on events that are observed from the first day of study drug administration through and including Day 28. A lower RP2D may subsequently be determined based on relevant toxicities that become evident after Day 28.

Table 7: Criteria for Defining Dose-Limiting Toxicity

Toxicity
Nonhematologic

 • Any \geq Grade 3 nonhematologic toxicity, EXCEPT the following: 
 – Transient (\leq 72 hours) abnormal laboratory values without associated clinically significant signs or symptoms. – Nausea, vomiting, and diarrhea adequately controlled with medical therapy within 48 hours. – Singular or nonfasting elevations in blood glucose (ie, blood glucose excursions will be considered toxicities if fasting blood glucose is elevated on 2 separate sequential occasions).
Hematologic

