3.1.3. Definition of Dose-Limiting Toxicities

A DLT will be defined as the occurrence of any toxicities in Table 2 occurring up to and including Study Day 28, except those with a clear alternative explanation (eg, disease progression) or transient (≤ 72 hours) abnormal laboratory values without associated clinically significant signs or symptoms based on investigator determination. All DLTs will be assessed by the investigator using CTCAE v4.03 criteria (NCI 2010). In order to be included in the tolerability review, subjects must have received the cohort-specific dose of INCB039110 and ibrutinib for at least 75% of the days during the 28-day surveillance period or have experienced a DLT. Additional subjects may be enrolled to achieve a minimum cohort size should withdrawal or dose interruptions/reductions result in subjects being nonevaluable.

Table 2: Criteria for Defining Dose-Limiting Toxicity

Toxicity
Nonhematologic

 • Any \geq Grade 3 nonhematologic toxicity, EXCEPT the following: 
 – Transient (\leq 72 hours) abnormal laboratory values without associated clinically significant signs or symptoms. – Nausea, vomiting, and diarrhea adequately controlled with medical therapy within 48 hours. – Singular or nonfasting elevations in blood glucose (ie, blood glucose excursions will be considered toxicities if fasting blood glucose is elevated on 2 separate sequential occasions).
Hematologic

 • Grade 3 thrombocytopenia with bleeding. • Grade 4 thrombocytopenia. • Febrile neutropenia ($ANC < 1.0 \times 10^9/L$ and fever $> 101^\circ F/38.5^\circ C$). • Grade 4 neutropenia that does not recover to \leq Grade 2 in \leq 3 days after interrupting study drug. • Grade 4 anemia unresponsive to treatment. 
Note: "INCB039110 is suspected to cause transient decreases in ANC as a result of margination; therefore, DLT rules require neutropenia to persist after holding INCB039110 for 2 to 3 days. If the clinical status of the subject allows, investigators are encouraged to wait 24 hours before starting growth factors, to determine if white blood cell margination is contributing to the degree of neutropenia."

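### The Phase 1 75% evaluability rule can remove subjects with early drug-related holds or reductions from the tolerability review, which biases the two-thirds criterion for the Phase 2 dose towards calling a dose tolerated.

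*Protocol*

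**What the plan says.** **Evaluability.** Protocol 4.1.1 states that "a subject must have received the cohort-specific dose of INCB039110 and ibrutinib for at least 75% of the days during the 28-day DLT surveillance period" to be included in the tolerability review. Protocol 5.5.2 repeats the rule and gives the one exception: "28-day surveillance period or have experienced a DLT". SAP 3.1.1 and 3.1.3 carry the same text.

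**Replacement.** Protocol 4.3.2 permits extra subjects, up to a minimum cohort of 6, "should withdrawal or dose interruptions/reductions result in a subject being nonevaluable". SAP 3.1.3 agrees: "Additional subjects may be enrolled to achieve a minimum cohort size should withdrawal or dose interruptions/reductions result in subjects being nonevaluable". Beyond the DLT exception, neither document distinguishes missed or reduced doses caused by the drugs from those with an unrelated cause.

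**Phase 2 dose.** Protocol 4.1.1 selects the dose "tolerated by at least two-thirds of subjects who did not require a dose reduction within the first 28 days of treatment".

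**Holds and reductions.** Protocol 5.5.1.1 says "Treatment with INCB039110 may be delayed up to 2 weeks (14 days) to allow for resolution of toxicity". Several rows of Table 4 repeat this limit ("Interrupt INCB039110 up to 14 days until the toxicity has resolved to" a stated grade). For platelets below 35 x 10^9/L and for Grade 4 ANC, the restart is at the next lower dose if the event is judged related to INCB039110.

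**DLTs.** Table 7 counts Grade 3 thrombocytopenia only with bleeding, Grade 4 thrombocytopenia, febrile neutropenia, and Grade 4 neutropenia only if it has not recovered to Grade 2 or better within 3 days of interrupting drug.

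**The concern.** The primary Phase 1 question is safety and tolerability, and the answer fixes the starting dose for about 60 Phase 2 subjects. A subject who cannot stay on the cohort dose because of the drugs, but whose event falls short of a DLT, is direct evidence on that question. Under the evaluability rule such a subject is treated like one who missed doses for an unrelated reason: left out of the review, and possibly replaced by someone who can stay on the dose. Exclusion then depends on the outcome being judged. The effect falls on the two-thirds criterion, because that criterion refers to dose reduction in the same 28 days.

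**Working it through.** **1. The threshold.** 0.75 x 28 = 21 days. At most 7 days off the cohort dose are tolerated, against a permitted hold of 14 days. A subject stepped down and not returned to the cohort dose within the window keeps 21 days only if the hold or step-down starts on Day 22 or later. So a non-DLT reduction that starts on Days 1 to 21 is not seen by the review.

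**2. Events that can lead there without a DLT.**
- Platelets of 25 to 35 x 10^9/L without bleeding. Protocol 5.5.1.2 puts Grade 4 below 25, so this is Grade 3 without bleeding and not a DLT under Table 7. Table 4 has a hold and, if related, a restart at the next lower dose.
- Grade 4 ANC that recovers to Grade 2 or better within 3 days. This is not a DLT, but Table 4 has a hold until Grade 1 or better and, if related, a lower dose.

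**3. The plan's own figure.** With p the true DLT rate, P(de-escalate) = P(X ≥ 3 of 6) + P(X = 2 of 6) x [1 − (1 − p)^3]. This gives 0.341, 0.469, 0.591, 0.700 and 0.790 at p = 0.25, 0.30, 0.35, 0.40 and 0.45, which is Table 14 exactly.

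**4. The two-thirds criterion.** Let d be the DLT rate and s the rate of drug-related, non-DLT loss of 8 or more days at the cohort dose, taken as mutually exclusive. Neither rate is in the documents; both are assumed. For a cohort of 6, two-thirds is 4, so the criterion is met if at most 2 do not tolerate the dose.
- Excluded and replaced: the visible failure rate is d/(1 − s).
- Counted as not tolerating: the failure rate is d + s.

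For d = 0.15 and s = 0.25 these are 0.15/0.75 = 0.20 and 0.40:
- P(X ≤ 2 of 6 at 0.20) = 0.262 + 0.393 + 0.246 = 0.901.
- P(X ≤ 2 of 6 at 0.40) = 0.047 + 0.187 + 0.311 = 0.544 (from unrounded terms).

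| d | s | Excluded and replaced | Counted as not tolerating |
|---|---|---|---|
| 0.15 | 0.25 | 0.901 | 0.544 |
| 0.20 | 0.10 | 0.872 | 0.744 |
| 0.20 | 0.15 | 0.853 | 0.647 |
| 0.20 | 0.20 | 0.831 | 0.544 |

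The last column is for six dosed subjects. If six evaluable places are still filled and the E excluded subjects are added to the denominator, the criterion needs 4 of 6, 5 of 7, 6 of 8 or 6 of 9 for E = 0, 1, 2, 3, and cannot be met for E ≥ 4. At d = 0.15 and s = 0.25, P(E) = 0.178, 0.267, 0.234, 0.156, and the chances of meeting it are 0.901, 0.655, 0.262, 0.262. The sum of products is 0.160 + 0.175 + 0.061 + 0.041 = 0.437. The direction is the same and the gap somewhat wider.

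**5. How often it would arise.** The chance that at least one of the first six subjects is excluded this way is 1 − (1 − s)^6: 0.469, 0.623 and 0.738 for s = 0.10, 0.15 and 0.20.

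**6. The DLT rule.** Table 3 counts only subjects with a DLT. At d = 0.15 and s = 0.25, P(de-escalate) is 0.115 if the excluded subjects are kept as no-DLT (p = 0.15) and 0.219 if they are replaced (p = 0.20). For that rule, replacement is the more cautious handling.

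**The case against.** The strongest counter-argument is that escalation runs on DLTs. A reader might infer that replacement makes de-escalation too rare, and set 0.219 (counted rate 0.20) against Table 14's 0.700 (rate 0.40). The documents do not support that. It compares the plan's rule with one that counts non-DLT holds as DLTs, which the plan does not contain. Step 6 shows that simply keeping these subjects as no-DLT would lower de-escalation. This part of the objection stands in full: Table 3 and Table 14 are not biased in the direction described here.

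Other points stand in part:
- Table 4 gives guidelines subject to clinical judgment, laboratory changes of 72 hours or less may be exempt, and 14 days is a maximum.
- Replacement is permitted, not automatic. Exclusion from the review, however, follows from the rule itself.
- Protocol 1.3.1 reports that neutrophil falls in healthy subjects generally resolved 24 to 48 hours after stopping, so long ANC holds may be uncommon. The platelet route and the early step-down remain.
- The broader Table 4 triggers (ANC of 1.0 x 10^9/L or below, platelets below 60) overlap partly with DLTs, and that row restarts at the same dose.
- All dosed Phase 1 subjects are in the safety run-in tables, the SAP tabulates events leading to interruption and reduction, and Protocol 8.8 provides for meetings to agree on tolerability. These make the events visible but leave the evaluability rule unchanged. Protocol 5.5.2 does allow a lower Phase 2 dose later, but for toxicities that become evident after Day 28.

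**Conclusion.** The concern holds for the two-thirds criterion and only there. The evaluability rule can remove the early drug-related reductions to which that criterion refers, so a dose looks better tolerated than it is. On the assumed rates, the chance of appearing to meet the criterion is overstated by 0.128 (0.872 against 0.744) to 0.357 (0.901 against 0.544).

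This rests on three assumptions. The rates d and s are illustrative, because the documents give no rate of sub-DLT holds or reductions. Tolerating is read as no DLT and no drug-related loss of 8 or more days at the cohort dose; the criterion itself names only reductions, so if long holds are not meant to count, s is the reduction share alone. The figures are for a cohort of 6, without the expansion to 9. The criterion's wording could also be read as limiting its denominator to subjects who were not reduced, in which case it would leave reduced subjects out by construction. That ambiguity is a further reason to clarify it.

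**What to change.** The sponsor should reconcile the 75% rule, Tables 4 and 7, and the two-thirds criterion in Protocol 4.1.1, 4.3.2 and 5.5.2 and in SAP 3.1.1 and 3.1.3. Specifically:

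1. Keep subjects who fall below 75% because of a drug-related event in the denominator of the two-thirds criterion, counted as not tolerating the cohort dose and reported beside the DLT count.
2. Do not let them fill DLT-evaluable places in Table 3 as no-DLT subjects. Those places can still be filled by further subjects.
3. State the numerator and denominator of the two-thirds criterion, and whether long holds count as well as reductions.
4. Add a listing of every nonevaluable or replaced Phase 1 subject with the reason. The visible part of SAP Appendix B lists disposition, dosing and DLTs, but not this. The listing is useful even if Phase 1 enrolment has ended.

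No change to any dose or to which events are DLTs is proposed. The cost is wording in three protocol sections and two SAP sections, plus one listing. The downside is that a dose may look less well tolerated, on the illustrative rates by a good deal.
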